#### Aim of the study

In this project, the effect of repeated cold application with dynamic compression with the Game Ready and a control group will be investigated. The influence of these interventions and their effects will be investigated after a primary total knee endoprosthesis operation during the hospital stay. The change in the following parameters is examined: questionnaire on everyday functions and patient satisfaction, joint circumference in mm, range of motion in degrees, skin temperature in C°, morphine consumption per day, pain perception with the VAS, the 10-meter walk test, timed-up-and-go and the length of the days of stay.

The aim is to determine the effects of cold application with dynamic compression in order to be able to make recommendations. The current scientific knowledge requires further studies to substantiate or refute effects that have already been established.

#### 3.2 Identification and description of the Investigational Medical Device

The Game Ready GR PRO 2.1 builds on the groundbreaking Game Ready technology and is a multimodality recovery device for professional users. The system can deliver ice-free cold treatment and intermittent pneumatic compression treatment, providing healthcare professionals with flexible options for different patients, procedures, injuries and rehabilitation stages.

Established principles such as PECH (pause, ice, compression, elevation) can be taken to a new level with the state-of-the-art Game Ready GR PRO 2.1. Cumbersome procedures for contrast treatment will be simplified with the compact, practical device. In addition, these can be monitored and controlled more consistently than conventional methods.

The unit consists of the following parts: the GRPro 2.1 control unit, connecting hose, the wrap (sleeve and heat exchanger), power supply and cable (see Figure 1). Only the cuff comes into contact with the patient's skin (see also Figure 2, right). The device is controlled via a touchscreen computer interface on the control unit. The user can choose between different treatment modalities and easily change and monitor the settings for treatment duration, temperature and compression. The double-acting (cryotherapy and compression) and anatomically designed Game Ready cuffs can be used specifically for specific parts of the body.

[figure not shown]

Figure 1 - Game Ready GR PRO 2.1 (<https://gameready.com/gr-pro-cold-therapy-unit/>)

This device is used for the treatment of post-traumatic, post-operative (medical and/or surgical) and acute injuries, as well as for the reduction of edema, swelling and pain when cold and compression are indicated.

According to the manufacturer, the following foreseeable serious adverse events and product defects may occur:

- tissue damage due to improper or too long use than described by the manufacturer,
- burning, itching, increasing swelling, pain, blisters, increasing redness, discoloration and other visible changes during treatment,
- Change in wound conditions (if the wrap is not applied over the bandage or clothing),
- Risk of electric shock (if other power supplies are used, housing parts are removed, or damaged cables and connecting hoses are used) and
- Device damage (if there is no or too hot water in the ice box, the device is lifted up by the lid, or wraps from other manufacturers have been used).

Despite the points listed above, the risk is classified as minimal, as no serious events can occur if used correctly and observed during application.

The following contraindications must be observed:

- patients with acute inflammatory phlebitis in the affected area,
- Patients with a history of or risk factors for deep vein thrombosis or pulmonary embolism in the affected area to be treated (including long periods of bedriddenness), -Patients with significant atherosclerosis or other ischemic vascular disease in the affected area,
- Patients with a condition in which increased venous or lymphatic reflux in the affected arm or leg is not desired (e.g. carcinoma),
- Patients with significant circulatory disorders in the affected area (e.g. due to previous frostbite, diabetes, arteriosclerosis or ischemia),
- Patients with acute paroxysmal cold hemoglobinuria or cryoglobulinemia.

Figure 2 - Game Ready GR PRO 2.1 (<https://gameready.com/gr-pro-cold-therapy-unit/>)

The manufacturer of the device is the company CoolSystems®, Inc. (Concord, California 94520, USA). The GR PRO 2.1 device is provided for the study by MTR Health & Spa AG.

### 3.3 Preclinical Evidence

A limited number of studies have already shown that cooling in combination with compression has been able to achieve a positive influence compared to non-cooling measures. These positive effects could be presented on both a subjective and an objective level (Su et al. 2012; Leegwater et al. 2012; Waterman et al. 2012; Murgier and Cassard 2014; Klaber, Greeff, and O'Donnell 2019; Nabiiev et al. 2018; Bellon et al. 2019).

### 3.4 Clinical Evidence to Date

Current research results regarding the cooling and compression effects, on which this study is based, have been presented in chap. 3.3.

#### Ache

Waterman and colleagues found a significant difference in pain perception after 6 weeks in favor of cryotherapy in combination with compression, in patients with anterior cruciate ligament reconstruction (Waterman et al. 2012). Other studies also found less subjective pain postoperatively when cryotherapy with dynamic intermittent compression is used than static pain (Murgier and Cassard 2014; Klaber, Greeff, and O'Donnell 2019).

#### Questionnaires

With regard to different questionnaires (Lysholm; assesses different functions of the knee, SF-36; assesses daily activity or SANE; assesses the disease state), no significant differences could be found at any time (Waterman et al. 2012).

#### Range of motion

When the average knee flexion movement is measured, strongly significant results could be found in favor of cryopneumatic intervention (Murgier and Cassard 2014).

#### Medication

In a study with patients who received cryopneumatic intervention after a total knee prosthesis, it was shown that significantly fewer narcotic drugs were consumed 2 weeks postoperatively compared to the control group who received ice with static compression (Su et al. 2012). This is also confirmed by a study by Murgier and Cassard, which found statistically significant results in the average morphine application. Although there were no statistical differences in tramadol use, there was a clear trend in favor of dynamically intermittent cryocompression (Murgier and Cassard 2014). These results confirm another study that used pneumatic compression and cryotherapy after elective hip arthroplasty (Leegwater et al. 2012).

#### Functional outcomes

Functional outcomes such as the 6-minute walk test or the timed-up-and-go test were not significantly different in a study after 2 and 6 weeks, but showed a trend in the intervention group (Su et al. 2012).

#### **Contentment**

In the study by Su and her colleagues, subjective satisfaction was also assessed and showed significant results in contrast to the control intervention (Su et al. 2012).

#### **Duration of stay**

Two studies found that a combination with pneumatic compression and cryotherapy can lead to a shorter hospital stay compared to a normal compression bandage or standardized cryotherapy (Leegwater et al. 2012; Klaber, Greeff, and O'Donnell 2019).

These still discursive study results suggest that further research is needed to provide clear evidence-based recommendations regarding pneumatic compression in combination with cryotherapy. Currently, no research with the product GR PRO 2.1 or any other device from Game Ready (Concord, California, USA) is taking place in the research laboratory of the University of Applied Sciences and Arts Southern Switzerland, Physiotherapy Graubünden and the Regional Hospital Surselva AG, [name].

### **3.5 Justification for the design of the clinical investigation**

In this study, the product Game Ready GR PRO 2.1 is used. This thermotherapy device is used as part of the intended application. The examiners apply cold including compression. The applied temperatures do not pose a danger to the test subjects at any time. The Game Ready GR PRO 2.1 generates temperatures from +5°C to +13°C. We will follow the following treatment program in this study: 48 hours after surgery, the intervention will start, if tolerable, with little compression (level 1 = 5-15 mmHg) and cooling at the coldest level tolerable by the participant (equivalent to program 2). The cooling should be perceived as "pleasant" by the participant. The intervention lasts one hour, of which 30 minutes are on and 30 minutes off cycles. The on cycle includes the duration of the intervention (cooling and compression), while the off cycles include the rest period. After 60 minutes, the device is removed. If compression is not tolerated, it can also be omitted (corresponds to program 1). The intervention is performed twice a day for the first four days after surgery. The coldest tolerable temperature level is determined anew with each treatment. The compression level can be increased depending on the participant. Medium compression may only be applied from the second day onwards (corresponds to programme 3). Doctors and physiotherapists can opt for cold treatments in their treatment. The question of whether the rehabilitation phase can be shortened or whether reintegration into everyday life can be increased by means of cooling applications including compression therapy is a legitimate question. These two parameters include not only objective values, but also subjective data.

### **3.6 Explanation for choice of comparator**

#### **Cooling/compression vs. control**

Two groups are compared to each other in order to compare the effects of cooling including compression compared to the control group. For example, the efficiency of cooling including compression is to be examined for rehabilitation capability. The following treatment program is adhered to: 48 hours after the operation, the intervention starts, if tolerable, with little compression (level 1 = 5-15 mmHg) and cooling at the coldest level tolerable by the participant (corresponds to program 2). The cooling should be perceived as "pleasant" by the participant. The intervention lasts one hour, of which 30 minutes are on and 30 minutes off cycles. The on cycle includes the duration of the intervention (cooling and compression), while the off cycles include the rest period. After 60 minutes, the device is removed. If compression is not tolerated, it can also be omitted (corresponds to program 1). The intervention is performed twice a day for the first four days after surgery. The coldest tolerable temperature level is determined anew with each treatment. The compression level can be increased depending on the participant. Medium compression may only be applied from the second day onwards (corresponds to programme 3). The control group does not receive any cooling in addition to standard therapy.

#### **Randomization**

In order to produce a high-quality study, the subjects are each assigned to a group, which are later compared with each other.

The assignment is carried out randomly. Randomization is guaranteed by drawing a lot.

### **3.7 Risk evaluation (Risk-to-Benefits rationale)**

There is minimal risk for the test subjects during cooling. The test subjects are expressly informed that they can stop the maximum tolerable cooling at any time. This also applies to integrated compression therapy. Furthermore, at least one examiner will be next to the subject during the cooling application in order to stop the intervention in the event of circulatory or other complaints. A fully equipped emergency kit is in the examination room at all times during the examinations. Since the intervention and measurements will take place on the premises of the Regionalspital Surselva AG, [name], first aid can be ordered directly in the event of circulatory and other problems. This information is communicated to the test persons (subject information). The device is used as recommended by the manufacturer.

### **3.8 Justification of the choice of the investigation population**

Furthermore, any injuries and illnesses were defined as an exclusion criterion in order not to take the risk of intervention. The listed criteria are also recommended by the manufacturer.

More information on securing the test subjects can be found in chap. 8.1.1.

## 4. CLINICAL INVESTIGATION OBJECTIVES

### 4.1 Overall Objective

In this study, the effect of a maximum of 2x60 minutes of body section cooling including compression per day on the subjective assessment of everyday functions [score] as well as patient satisfaction [cm] and physiological inflammation parameters such as swelling [mm],

The pain scale [cm], skin temperature [°C], range of motion [degrees], morphine consumption [number] and length of stay [days] were examined. In addition, two assessments are used to assess everyday function: the 10-metre walk test [sec] and the timed-up-and-go [sec]. The effects of thermal application are compared to a control group and compared preoperatively, postoperatively (4th postoperative day) and after 6 weeks after surgery. The aim is to substantiate the state of scientific knowledge and to provide therapists and physicians with further insights. This study can benefit all those who work with patients after primary total knee arthroplasty.

### 4.2 Primary Objective

In this project, the effect of postoperative cooling on physiological parameters is measured and compared with the control group.

- Physical Function [Score]
- Patient satisfaction [cm]
- Joint circumference [mm]
- Range of motion [degrees]
- Skin temperature [°C]
- Morphine consumption [number]
- Visual analog scale [cm]
- Length of stay [days]
- 10-meter walk test [sec]
- Timed-Up-and-Go [sec]

### 4.3 Secondary Objectives

-

### 4.4 Safety Objectives

No short-term risks are to be expected from this study other than those discussed so far.

## 5. CLINICAL INVESTIGATION OUTCOMES

### 5.1 Primary Outcome

This study aims to investigate the effects of cryotherapy with intermittent dynamic compression with Game Ready during a hospital stay. The preoperative measurement is the baseline, the 4th postoperative day is the primary endpoint and the measurement 6 weeks postoperative is declared as follow-up. The following parameters are examined for this purpose:

#### Questionnaire Physical Function [Score]

To determine the subjective assessment of physical function, the KOOS questionnaire is handed out, evaluated and documented. The KOOS questionnaire is highly valid for knee complaints and refers to the subjective impression of the patients (Roos and ToksvigLarsen 2003). The measurement moments take place preoperatively, on the 4th postoperative day and 6 weeks postoperatively.

#### Patient satisfaction [cm]

In order to evaluate the patient satisfaction of the intervention group (Game Ready), the test subjects are asked the question "How satisfied are you with the cooling intervention?" immediately after the intervention. With the help of the Visual Analog Scale, the test subjects rate their satisfaction with a number between 0 (not at all satisfied) and 10 (maximally satisfied). The measurement moments take place twice a day (each time after the cooling intervention) during the

hospital stay.

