----------------------------------	---

Objective(s):	
In this study, the effect of repeated cold application with dynamic compression with the Game Ready and a control group will be investigated. The influence of these interventions and their effects will be investigated after a total knee endoprosthesis operation has been performed during the hospital stay. The change in the following parameters is examined: questionnaire on everyday activity and patient satisfaction, joint circumference in mm, skin temperature in C°, range of motion in degrees, morphine consumption in number per day, Pain sensation with the VAS, the length of the days of stay, the 10-meter walking test and the timed up-and-go in seconds.
 
The aim is to determine the effects of cold application with dynamic compression in order to be able to make recommendations. The current scientific knowledge requires further studies to substantiate or refute effects that have already been established.

Outcome(s):	
Primary outcomes
 
 
-Questionnaire Everyday Activity [Score]
 
-Patient satisfaction [cm]
 
-Joint circumference [mm]
 
-Range of motion [degrees]
 
-Skin temperature [°C]
 
-Morphine consumption [number]
 
- Visual analog pain scale [cm]
 
-Duration of stay [days]
 
-10-meter walk test[s]
 
-Timed-Up-and-Go [s]
 

Design:	Randomized, controlled trial

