### 2. *Running the Test Log*

Test log	
Cooling group	Control group
Visit 1: Screening and baseline preoperatively: information, written consent, examination of /Exclusion criteria, health questionnaire Physical Function [Score] Joint circumference [mm] Range of motion [degrees] Skin temperature [°C] Visual Analog Pain Scale [cm] 10-meter walk test [sec] Timed-up-and-Go [sec]	Visit 1: Preoperative screening and baseline information, written consent, examination of /Exclusion criteria, health questionnaire Physical Function [Score] Joint circumference [mm] Range of motion [degrees] Skin temperature [°C] Visual Analog Pain Scale [cm] 10-meter walk test [sec] Timed-up-and-Go [sec]
Daily cooling intervention In addition to the usual physiotherapeutic treatment: Daily Cooling and compression. One detailed treatment description can be found in chap. 8.1.1.	Daily Control Intervention In addition to the usual physiotherapeutic Treatment: No refrigeration (see chapter 8)
Visit 4: Follow up 4th postoperative day Physical Function [Score] Joint circumference [mm] Range of motion [degrees] Skin temperature [°C] Visual Analog Pain Scale [cm] Patient satisfaction [cm] 10-meter walk test [sec] Timed-up-and-Go [sec]	Visit 4: Follow up 4th postoperative day Physical Function [Score] Joint circumference [mm] Range of motion [degrees] Skin temperature [°C] Visual Analog Pain Scale [cm] 10-meter walk test [sec] Timed-up-and-Go [sec]

Visit 5: Follow up 6 weeks postoperatively
 
Physical function [Score] Joint circumference [mm]
 
Range of motion [degrees]
 
Skin temperature [°C]
 
Visual Analog Pain Scale [cm]
	
Visit 5: Follow up 6 weeks postoperatively
 
Physical function [Score] Joint circumference [mm]
 
Range of motion [degrees]
 
Skin temperature [°C]
 
Visual Analog Pain Scale [cm]

10-meter walk test [sec]
 
Timed-up-and-Go [sec]
 
Length of stay [days]
 
Morphine consumption [number]
	
10-meter walk test [sec]
 
Timed-up-and-Go [sec]
 
Length of stay [days]
 
Morphine consumption [number]

Test log	
Rounds	Time exposure

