#### Patient satisfaction [cm]

In order to evaluate the patient satisfaction of the intervention group (Game Ready), the test subjects are asked the question "How satisfied are you with the cooling intervention?" immediately after the intervention. With the help of the Visual Analog Scale, the test subjects rate their satisfaction with a number between 0 (not at all satisfied) and 10 (maximally satisfied). The measurement moments take place twice a day (each time after the cooling intervention) during the hospital stay.

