## **11. STATISTICAL METHODS**

### **11.1 Hypothesis**

Physical Function [AU]

H0: The use of cryotherapy with intermittent dynamic compression has no positive effect on the physical functions of patients after a total knee arthroplasty.

H1: The use of cryotherapy with intermittent dynamic compression has a positive effect on the physical functions of patients after a total knee arthroplasty.

Patient satisfaction [cm]

H0: The use of cryotherapy with intermittent dynamic compression has no positive effect on patient satisfaction of patients after a total knee arthroplasty.

H1: The use of cryotherapy with intermittent dynamic compression has a positive effect on patient satisfaction of patients after a total knee arthroplasty.

Joint circumference [mm]

H0: The joint circumference is not reduced by cryotherapy with intermittent dynamic compression compared to the control group during a hospital stay.

H1: The joint circumference is reduced by cryotherapy with intermittent dynamic compression compared to the control group during a hospital stay.

Skin temperature [C°]

H0: The skin temperature is not reduced by cryotherapy with intermittent dynamic compression compared to the control group during a hospital stay.

H1: The skin temperature is reduced by cryotherapy with intermittent dynamic compression compared to the control group during a hospital stay.

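### Patient satisfaction is a primary outcome with its own hypothesis but is collected only in the Game Ready arm, so it cannot be compared between arms

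*Combined protocol and SAP*

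**What the plan says.** **Status of the outcome.** The Synopsis puts "Patient satisfaction [cm]" in its list of primary outcomes. Section 4.2 lists it under an objective in which "the effect of postoperative cooling on physiological parameters is measured and compared with the control group". Section 4.1 also names satisfaction among the effects studied and says that the effects are set against a control group. Section 11.1 gives it an H0/H1 pair; under H1 the treatment "has a positive effect on patient satisfaction of patients after a total knee arthroplasty". Section 3.4 (Contentment) supports it with a cited trial in which "subjective satisfaction was also assessed and showed significant results in contrast to the control intervention".

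**Measurement.** Sections 5.1 and 9.2.1 say: "In order to evaluate the patient satisfaction of the intervention group (Game Ready), the test subjects are asked the question". The item asks how satisfied the patient is with the cooling, scored 0 to 10. On timing: "The measurement moments take place twice a day (each time after the cooling intervention) during the hospital stay". Section 3.6 says of the comparator: "The control group does not receive any cooling in addition to standard therapy".

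**Visit tables.** In the two-column test log of Section 9.1, the cooling column for the 4th postoperative day contains "Patient satisfaction [cm] 10-meter walk test [sec]". The control column for the same visit goes straight from the pain scale to the walk test. The second table in Section 9.1, on time commitment, has one entry for satisfaction at that visit and does not separate the arms.

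**Analysis.** Section 11.4.2 plans a repeated-measures model with an arm factor and a Time factor at baseline, day 4 and 6 weeks. Section 11.4.3 contrasts sides over the same times. The Synopsis also gives a two-way repeated-measures analysis with a Time factor. No other between-arm test is named. Length of stay is a single count of hospital days (Section 5.1).

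**The concern.** A claim that a treatment improves satisfaction needs a comparator. The plan labels the outcome primary and states a hypothesis for it, but it collects nothing from controls, and the question could not be put to them as worded.

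If this stays, a stated primary hypothesis either goes unanswered or is judged from high or low scores in one arm, given by unblinded patients about a device they have just used. Control ratings from the hospital stay cannot be recovered later, so the decision has to be made while patients can still be asked.

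Length of stay raises a milder version of the same question. It has a hypothesis against control (Section 11.1), but the only model with an explicit arm factor does not accommodate it.

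**Working it through.** The point rests on who is measured and when. It does not depend on the sample-size calculation, so the planned total of 28 enters only as the arm sizes.

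**Inputs**
- 14 patients per arm, 28 in total (Synopsis; Section 6.1).
- Two sessions a day on four days (Section 9.1, time-commitment table).
- Three Time levels and two arms (Section 11.4.2).
- Ten primary outcomes (Synopsis; Section 4.2) and nine H0/H1 pairs (Section 11.1).

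**1. Satisfaction ratings by arm**
- Control: 14 × 0 = 0.
- Game Ready, rated after each session (Sections 5.1, 9.2.1): 14 × (4 × 2) = 14 × 8 = 112 at most. This is an upper bound. It takes four full treatment days at face value, while Section 8.1.1 starts treatment 48 hours after surgery yet also places it in the first four days after surgery. Those statements need reconciling.
- Game Ready, one day-4 entry (Section 9.1): 14 × 1 = 14.

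The between-arm estimate is the device mean minus the control mean, with variance s_D²/n_D + s_C²/n_C. With n_C = 0, neither the control mean nor the second variance term exists. Enrolling more patients under the same procedures leaves n_C at 0.

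**2. Satisfaction in the planned model**

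The model has 2 arms × 3 times = 6 cells. Satisfaction has no baseline value, no 6-week value and no control value, so at most 1 of the 6 cells is filled (device arm, day 4). No effect of arm, of time, or of arm by time can be estimated.

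**3. Length of stay**

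An outcome measured at every visit supplies 28 × 3 = 84 values. Length of stay supplies 28 × 1 = 28, one per patient in both arms. Time and arm-by-time effects are undefined for it, but a plain two-group comparison is possible. The plan does not name one.

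**4. Morphine**

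Section 5.1 counts preparations per day, and the hypothesis in Section 11.1 concerns the hospital stay. These agree. No rule turns the daily counts into one number per patient.

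**5. What is unaffected**

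10 − 3 (satisfaction, length of stay, morphine) = 7 outcomes: physical function, circumference, range of motion, skin temperature, pain, walk test and Timed-Up-and-Go. Section 9.1 schedules all seven in both arms at all three times.

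**The case against.** **Satisfaction may have been meant only as a device-acceptability item.** Section 5.1 openly says that it evaluates the Game Ready group. The satisfaction hypothesis does not name the control group, whereas seven of the nine pairs do. The comparison sentence in Section 4.2 speaks of physiological parameters. This is a fair reading of the intent, and it favours relabelling. It does not remove the defect. Section 4.2 includes satisfaction in its list, and Section 4.1 names it alongside the physiological measures before stating the comparison with control. A positive effect cannot be shown without a comparator. If the item is descriptive, the primary label and the H0/H1 are wrong.

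**A competent analyst would run a two-group test on length of stay.** Probably so, and the data will exist in both arms. A reader might infer that length of stay is untestable in the same way as satisfaction. The documents do not support that: only the specification is missing.

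**Morphine.** A reader might infer that its timing contradicts itself, because the visit tables list it only at 6 weeks. The entry stands beside length of stay, which is complete at discharge, so it plausibly marks when hospital totals are entered. Only the missing per-patient summary stands.

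**Conclusion.** The concern holds for satisfaction: one of ten primary outcomes, and one of nine hypothesis pairs, cannot be tested between arms because no control data are planned. This follows from the documents' own definitions and needs no assumption about effect size or variance. The conflict between per-session ratings and a single day-4 entry is a further gap, since it leaves open whether there are up to 112 ratings or 14.

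Length of stay and the morphine summary are secondary specification gaps.

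The point should be fixed, but it does not threaten the trial as a whole. A reader might infer that the primary analysis fails or that 28 patients are too few. Neither follows. Seven outcomes have the planned data in both arms at all three times. The figure showing the sample-size inputs is not available here, and the sample size has no bearing on missing control ratings. Wording alone can cure the satisfaction defect.

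**What to change.** **Satisfaction: choose one.**

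(a) Remove it from the primary between-arm outcomes in the Synopsis, Section 4.2 and Section 5.1, and align Section 4.1. Delete its H0/H1 in Section 11.1. Report device-arm scores descriptively, stating which rating or summary of ratings is used. Cost: wording only, but satisfaction is given up as an efficacy claim.

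(b) Ask both arms one treatment-neutral question, about satisfaction with the treatment received, at the existing day-4 visit. Compare the arms once, and name the control group in the hypothesis. Update Sections 5.1 and 9.2.1 and both tables in Section 9.1, and check the data collection form. Cost: one new question for 14 controls. It measures a different construct from satisfaction with cooling, and it remains open to bias because participants cannot be blinded (Section 6.2.2).

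Under either option, reconcile the timing between Sections 5.1/9.2.1 and Section 9.1. Either may need ethics committee approval as a substantial amendment (Section 2.9).

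**Length of stay.** State in Section 11.4.2 that it lies outside the Time-factor model and is compared once between arms on one value per patient, for example by a rank-sum test with an estimated difference and 95% CI. Cost: a sentence.

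**Morphine.** Name one in-hospital summary per patient, consistent with the daily count in Section 5.1 and the hypothesis in Section 11.1. Cost: a sentence.
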